Subjects will be excluded from this study who have renal impairment because of potential risks associated with the use of exenatide in patients with this problem. Subjects will be enrolled into this study only if the values for renal tests (Creatinine, BUN) are within normal limits. Given the warning concerning the association of exenatide treatment with pancreatitis, subjects will not be enrolled into this study if they have a history of pancreatitis or lipase above the upper normal limit. Subjects with a history of thyroid cancer or other thyroid disease will be excluded from this study because of studies showing that exenatide increases the risk of the occurrence of thyroid cancer in animals. Subjects taking warfarin will be excluded to minimize the risk of a drug interaction.

Diabetic patients will be excluded from this study because the use of antidiabetic medications including the sulfonylureas and metformin may increase the incidence of adverse effects associated with the use of exenatide. Of particular concern is the possibility that the use of antidiabetic agents may increase the risk of hypoglycemia occurring in individuals receiving injections of exenatide. Finally, the administration of exenatide to a diabetic patient would be a therapeutic intervention that should occur only in coordination with their other health care providers.

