We will screen for suicidality using the Columbia-Suicide Severity Rating Scale and the MINI Neuropsychiatric Interview. Subjects with a MINI suicidality score greater than 8 (low risk) will be excluded. Subjects who report any active suicidal thoughts or behavior as measured the C-SSRS will be excluded from participation. In addition to excluding active suicidality, the MINI will be used to rule out subjects who have psychiatric conditions that may increase the risk of the occurrence of suicidal thoughts or behavior (e.g., major depression, bipolar disorder). Assessment and scoring of suicide rating scales will be conducted in real-time while the subject is present. Suicidality will be assessed by trained clinical staff including study MDs, a psychologist, a nurse, and a

mental health counselor. If subjects are found to be at risk for self harm, study staff will work with the subject to develop a safety plan that could include escorting the subject to the BMC ED or calling BEST.

Incidental findings

There is a possibility for clinically significant abnormal findings on the ECG and blood laboratory tests. Clinically significant abnormal findings will be communicated to study subjects with a recommendation to follow-up with primary care or specialized care.

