7.2 Subject Exclusion

7.3 Criteria

An individual who meets any of the following criteria will be excluded from participation in this study:

An individual who meets any of the following criteria will be excluded from participation in this

The Effects of Exenatide, a GLP-1 Agonist, on Alcohol Self-Administration in Heavy Drinkers
Version 1.8 10.5.20

study:

1. Seeking treatment for alcohol problems.
2. Clinical Institute Withdrawal Assessment at ≥ 10
3. DSM-5 diagnosis of current major depression, bipolar disorder, schizophrenia, bulimia/anorexia, dementia, or a substance use disorder other than alcohol, nicotine, marijuana or caffeine.
4. If female, pregnant, nursing, have plans to become pregnant.
5. If female, does not agree to use an accepted form of birth control.
6. Has a medical contraindication to the use of exenatide.
7. Has medical or mental condition for which further alcohol exposure at the planned dose range would be contraindicated.
8. Current risk of suicidality (MINI suicidality score greater than 8 (low risk) or Yes to the ideation question #4 of the C-SSRS).
9. BMI is less than 18 or greater than or equal to 30.
10. History of diabetes.
11. Baseline hemoglobin A1c $\geq 6.5\%$
12. Baseline nonfasting glucose >200
13. Significantly elevated serum lipase levels.
14. Impaired renal function (GFR <80 mL/min).
15. Pancreatitis, gastroparesis or other severe gastrointestinal disease.
16. Has had gastric bypass surgery
17. Subject is currently taking warfarin.
18. Has received alcohol counseling or other non-pharmacologic intervention to treat AUD in the past 90 days.
19. Has taken medications that are used to treat AUD in the past 90 days.
20. Subjects with a history of thyroid cancer or other thyroid disease.
21. Has urine toxicology results positive for cocaine, opioids, amphetamines, buprenorphine, methadone, or methamphetamines.
22. Prior history of anaphylaxis or angioedema with another GLP-1 receptor agonist.
23. Prior use of exenatide
24. Liver function values AST or ALT are twice the normal limit
25. Unable to comfortably abstain from nicotine for a period of 8 hours.
26. Has COPD, history of solid organ transplant, sickle cell disease, severe heart disease or other health condition for which exposure to COVID-19 represents an unreasonable risk as determined by the study staff physician using accepted COVID-19 guidance (e.g. Centers for Disease Control, etc.).
27. Subject has prior history of Drug-induced thrombocytopenia

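### Section 6.1 sets mandatory safety exclusions (lipase, C-SSRS, renal, pancreatitis) that the numbered exclusion list repeats in looser or different form, and nothing says which text governs

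*Combined protocol and SAP*

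**What the plan says.** The part of Section 6.1 on protections against risk gives enrollment rules in mandatory language. It introduces the lipase rule with "Given the warning concerning the association of exenatide treatment with pancreatitis" and continues that "subjects will not be enrolled into this study if they have a history of pancreatitis or lipase above the upper normal limit". The sentence before this requires creatinine and BUN to be normal. Under the suicidality heading, Section 6.1 says "Subjects with a MINI suicidality score greater than 8 (low risk) will be excluded" and then "Subjects who report any active suicidal thoughts or behavior as measured the C-SSRS will be excluded from participation".

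The numbered list in Sections 7.2/7.3 opens with "An individual who meets any of the following criteria will be excluded from participation in this study". Criterion 8 reads "Current risk of suicidality (MINI suicidality score greater than 8 (low risk) or Yes to the ideation question #4 of the C-SSRS"). Criterion 13 reads "Significantly elevated serum lipase levels". Criterion 14 defines renal impairment as GFR under 80 mL/min. Criterion 15 names pancreatitis alongside other gastrointestinal disease and does not say whether a past episode counts.

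Section 3.1 ends by committing the study to compliance with the protocol as a whole. Section 11.3 lists an Eligibility CRF. Appendix A lists an Eligibility Checklist at the first trial visit and an eligibility confirmation at both trial visits. The content of these forms is not shown.

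**The concern.** These are safety limits for people who will receive exenatide and alcohol together. Section 6.3 rests its favorable risk judgment on the protections described in Section 6. A numbered exclusion list is normally what screening staff work from and what an eligibility form is built on. If the list is the less protective text, screening from it would not deliver the protections that the risk assessment relies on. No section ranks the two texts, cross-refers between them, or tells staff to apply the stricter rule.

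**Working it through.** No formula applies, so the check sets the two texts side by side.

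| Topic | Section 6.1 | Numbered list | Relation |
|---|---|---|---|
| Lipase | Any value above the upper normal limit | Criterion 13: an adjective, no number | Explicit limit against an unquantified term |
| C-SSRS | Any active ideation or any behavior | Criterion 8: Yes to ideation question #4 only | List is narrower and names no C-SSRS behavior item |
| Renal | Creatinine and BUN both normal | Criterion 14: GFR under 80 mL/min | Different measures; BUN is absent from the list |
| Pancreatitis | Any history | Criterion 15: the disease, timing unstated | List leaves past episodes open |
| MINI suicidality | Score above 8 | Criterion 8: score above 8 | Same |

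1. **Lipase.** A subject just above the upper normal limit is barred by Section 6.1. Under criterion 13 the outcome depends on what the reader takes the adjective to mean. Of the five blood-test exclusions in the list (criteria 11, 12, 13, 14 and 24), four state a limit and lipase does not.
2. **C-SSRS.** A subject who reports suicidal behavior but does not answer Yes to question #4 is barred by Section 6.1 and not by the C-SSRS part of criterion 8. The missing behavior item is visible on the page. How far question #4 falls short of all active ideation cannot be judged, because the instrument is not reproduced.
3. **Renal.** A subject with GFR of 80 or more but raised BUN passes criterion 14 and fails Section 6.1. In the other direction, Section 6.1 sets no GFR limit. Neither rule contains the other.
4. **Pancreatitis.** A subject with a resolved past episode is barred by Section 6.1. Criterion 15 can be read either way.
5. **Precedence.** The list's opening sentence makes each item sufficient for exclusion. It does not say that the list is complete or that it overrides Section 6.1. The remaining sections and both appendices contain no ranking statement.

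The identical MINI rule shows that the two sections can carry the same limit. Within criterion 8, only the C-SSRS part departs from Section 6.1.

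**The case against.** The strongest reply is that the rules are cumulative. Section 6.1 is mandatory, the list is not declared exhaustive, and nothing in the list authorizes enrolling a person whom Section 6.1 bars. Staff who apply the whole protocol would exclude every subject described above. For lipase, Section 6.1 could even be read as supplying the definition that criterion 13 lacks. This stands, and it makes the problem conditional on how screening is done.

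Other safeguards also stand. The MINI cut-off applies in both places. Criterion 3 removes current major depression and bipolar disorder. Criteria 6 and 7 allow exclusion for a contraindication to exenatide or to alcohol. Suicidality is rated by trained clinical staff, "Assessment and scoring of suicide rating scales will be conducted in real-time while the subject is present", and the C-SSRS is given at all three visits. The MINI suicidality items are not shown, so that score may capture some behavior. These measures reduce the consequence, but they do not restore the fixed Section 6.1 limits.

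A reader might infer three stronger things that the documents do not support:

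- **That the two sections issue opposing instructions.** They do not. One is silent or vaguer where the other is explicit.
- **That ineligible subjects will be enrolled.** The Eligibility CRF and Checklist may already carry the Section 6.1 wording.
- **That the problem can be sized by counting screening decisions:** 72 for lipase, or up to 72 + 36 + 36 = 144 for the C-SSRS. These counts restate the sample size. The larger one also assumes that criterion 8 is re-applied at each trial, which is not stated, and that nobody drops out.

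**Conclusion.** The inconsistency is real and covers four exclusions. The list is narrower on the C-SSRS, unquantified on lipase, based on a different measure for renal function, and unclear on past pancreatitis. Its practical effect depends on staff or forms using the list alone, and the documents do not settle whether they will.

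The number of subjects falling between the two texts is unknown. The sample size, power and planned analyses are unaffected. This is a safety-eligibility inconsistency rather than a design flaw. It ranks between a minor correction and one that should be made: the possible error runs in the less protective direction, and the correction is cheap.

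**What to change.** Amend the list to carry the Section 6.1 limits:

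- **Criterion 8:** keep the MINI part. Replace the C-SSRS part with any active suicidal ideation or any suicidal behavior, naming the C-SSRS items and the look-back period.
- **Criterion 13:** serum lipase above the upper normal limit.
- **Criterion 14:** keep the GFR limit and add creatinine or BUN outside normal limits.
- **Criterion 15:** current or past pancreatitis.

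Match the Eligibility CRF and the Eligibility Checklist to this wording. If the sponsor intends the list's limits instead, amend Section 6.1 and give criterion 13 a numeric cut-off.

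No new data are needed. Appendix A already schedules lipase, creatinine, BUN and medical history at baseline, and the C-SSRS at every visit.

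The cost is a short amendment and possibly a few more screen failures. If Section 6.1 already binds in practice, there are none. As a rough guide from Section 12.2, 28 completers need 28/0.85 = 32.9, so 33 randomized, at 15% non-completion, or 28/0.80 = 35 at 20%. The planned 36 therefore leaves 36 − 33 = 3 or 36 − 35 = 1 to spare before more screening is needed. The inputs are themselves approximate, and subjects later dropped from the primary analysis for nausea are not counted.

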More than 16 million adults suffer from Alcohol Use Disorder (AUD) in the United States⁸. The economic burden of this is estimated to be 249 billion dollars and approximately 88,000 Americans die from alcohol-related causes each year⁹. Untreated AUD is associated with an increased risk of accidents, injuries, suicide, and worsening of other health comorbidities¹⁰ and it is the fourth most preventable cause of death in the US⁹. Treating addiction more effectively has become a priority of national importance and the Surgeon General has urged researchers to undertake testing of new treatments to combat addiction¹¹. The present study is intended to answer the call for accelerating drug development for AUD by exploring the potential to re-purpose an existing drug as a treatment for AUD⁶⁻⁷.

Rationale for developing exenatide as an agent to treat AUD

GLP-1 is an endogenous peptide that regulates blood glucose by decreasing the rate of gastric emptying, promoting pancreatic beta cell activity if blood glucose levels are elevated, reducing glucagon release, and producing satiety for food¹³. Peptides that share structural similarities to GLP-1 have been synthesized including exenatide (synthetic Exendin-4) and liraglutide that are resistant to the GLP-1 metabolizing enzyme dipeptidyl peptidase IV¹³⁻¹⁴. There is now substantial preclinical evidence that these GLP-1 agonists can attenuate behaviors that model both the consumption and seeking of several commonly abused substances including alcohol^{7-8,10-11}, cocaine¹⁵, and nicotine¹⁶. Consistent with the idea that GLP-1 agonists are acting on overlapping pathways that regulate both food and drug intake, these compounds have been found to attenuate the reinforcing actions of food^{6,17-18}. Both Exendin-4 and liraglutide have been shown to reduce alcohol consumption by rodents^{7,8-11}. The administration of these drugs attenuates alcohol-induced place preference^{7,10} indicating that they reduce the rewarding effects of alcohol. Treatment with Exendin-4 blocks increases in

The Effects of Exenatide, a GLP-1 Agonist, on Alcohol Self-Administration in Heavy Drinkers
Version 1.8 10.5.20

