There is a warning that post-marketing data indicate that acute pancreatitis including necrotizing pancreatitis and hemorrhagic pancreatitis (fatal and non-fatal) have occurred in association with exenatide administration. A precaution exists stating that there is an increased risk of hypoglycemia occurring in patients taking exenatide in combination with sulfonylureas. The administration of pharmacologic doses of GLP-1 were not found to increase the incidence of occurrence of hypoglycemia in fasting healthy subjects⁵⁷. Exenatide may produce nausea and vomiting that can be problematic in patients with impaired renal function. This drug was not well tolerated in patients with end-stage renal disease who were undergoing dialysis. It is advised that exenatide be used with caution in patients with severe renal impairment. Some reports of allergic reactions have been reported during post-approval use of exenatide including injection-site reactions, generalized pruritus and/or urticaria, macular or papular rash, angioedema, anaphylactic reaction.

In a study of the effects of monotherapy with exenatide 10 mcg twice daily over a period of 24 weeks, 10% of subjects experienced nausea vs 0% of those who received placebo. Three percent of subjects vomited vs. 0% of those who received placebo⁵⁸. In one study 65% of healthy subjects developed nausea following injection of 10 mcg dose exenatide when they were allowed to eat a standardized meal 60 minutes after the administration of this drug⁵⁹. In a dose ranging study of exenatide monotherapy with type-2 diabetics, nausea was reported by 13% of subjects receiving .1 mcg/kg dose, 0% of subjects receiving .2 mcg/kg dose, 29% of subjects receiving .3 mcg/kg dose, 60% of subjects receiving .4 mcg/kg dose, and 14% of subjects receiving placebo⁶⁰. There is a warning that thyroid C-cell tumors have been observed to occur in female rats receiving extended release treatment with exenatide. Also, exenatide has produced developmental toxicity when administered to pregnant rats.

Table 3. Combination therapy vs. placebo		
Adverse effect	Placebo	Combination Therapy
Nausea	18%	44%
Vomiting	4%	13%
Diarrhea	6%	13%
Feeling jittery	4%	9%
Dizziness	6%	9%
Headache	6%	9%
Dyspepsia	3%	6%
Asthenia	2%	4%
Gastric Reflux	1%	3%
Hyperhidrosis	1%	3%

Risks of Phlebotomy, medication injection, and pinprick for blood glucose test

These procedures may cause pain, bruising, lightheadedness, fainting and on rare occasions, infection.

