Study randomization: Subjects will be randomized to a crossover sequence of drug exposure. Subjects will be assigned to one of two groups, with one group receiving exenatide in the alcohol challenge Trial #1 and the other receiving exenatide prior in the alcohol challenge Trial #2. Randomization of subjects will be accomplished using a stratified randomization procedure that will allow for between-group balance for drinking status (heavy vs. very heavy). Heavy drinking is defined as ≥ 21 and < 35 standard drinks per week for men, and ≥ 14 and < 28 standard drinks per week for women. Very heavy drinking is defined as ≥ 35 standard drinks per week for men, and ≥ 28 standard drinks per week for women. This stratified randomization will minimize the possibility that the order of study drug administration seems to influence outcomes when order effects are actually related to differences in severity of drinking between the two groups of subjects who are receiving the study medication in a different order. On the day of randomization, subjects will undergo an alcohol breath test, urine drug screening, assessment of concomitant medications, and the TLFB. Subjects who have purposefully abstained from drinking and achieved 14 days of abstinence prior to the challenge will be discontinued from participation for ethical reasons⁴⁹.

Alcohol Challenge Trials 1 & 2: Subjects will return to the laboratory within 14 days of the baseline assessment to complete the alcohol Challenge Trial #1. Prior to the visit, subjects will complete a COVID-19 symptom screening questionnaire following standard of care procedures. If the subject does not complete the screening questionnaire before arriving in clinic, study staff will administer the questionnaire outside of the clinic at a 6-foot distance. If the subject answers 'yes' to any question about known COVID symptoms, their in-clinic visit will be cancelled and they will be advised to contact their PCP and/or get tested at a testing center. Concomitant medications, urine drug screening, Blood Alcohol Concentration (BAC) will be assessed to determine eligibility to proceed with the challenge. A BAC reading of 0.000 is required at each visit to continue with the study procedures. For safety reasons, subjects will be asked to arrange transportation plans that does not include driving themselves home.

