Subjects will be given a priming drink designed to increase the subject's blood alcohol level (BAL) to 0.03g/dl, using the alcohol of their choice that is 24% Alcohol By Volume (ABV) or greater. Drinks will be mixed with a sugary mixer (3:1 Mixer:Alcohol) to preclude the occurrence of hypoglycemia. The volume of alcohol will be calculated using an online tool developed by UW-Madison (<http://dionysus.psych.wisc.edu/WebCMS/baccalc.htm>) based on a formula described by Watson⁵¹. The subjects will be asked to drink the priming drink over a period of 5 minutes. The purpose of the priming drink is to normalize drinking in the laboratory.

Absorption period. Subjects will be observed for 40 minutes following the priming dose of alcohol. This period will provide ample time for subjects to reach the target BAC. Breathalyzer readings will be completed at 10 minutes intervals.

Alcohol self-administration Blocks 1 and 2. In each of the alcohol self-administration Blocks, subjects will be presented with four drinks, each mixed to raise their BAC by 0.0125g/dl. They will be told that they can either consume the desired number of drinks over the following 60 minutes, or they will receive the equivalent dollar amount of the cost of each drink (\$3.00) they did not consume. At the end of each 1-hour session the drinks will be removed and the volume of alcohol remaining will be measured with a graduated cylinder. Cravings will be assessed using the AUQ and VAS every 30 min during the self-administration blocks. BAC levels will be obtained at the end of the Block 2 session as will blood glucose levels. Blood glucose levels will be measured at the end of Block 2 using a glucometer and blood obtained from a pinprick sample. If the subject is found to be hypoglycemic (glucose < 70 mg/dL), staff will give the subject orange juice and re-test in 30 minutes. If the subject is found to be hyperglycemic (glucose > 300 mg/dl), staff will escort the subject to the BMC emergency department for evaluation. At the end of this session subjects will also be asked to rate their experience of nausea using a visual analog scale developed to assess nausea in an emergency department⁵². Subjects will be assessed for safety prior to subjects leaving the laboratory. Subjects will not be released until their BAC is below 0.04 g/dl and they are not behaviorally impaired.

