12.2 Sample Size Determination

A group size of 28 completers was selected for use in this study based on an assumed effect size of 0.7 suggested by similar alcohol self-administration studies with amount consumed as the primary outcome^{42,44}. This effect size is in the range we found for the anticonvulsant zonisamide used in a similar alcohol self-administration study⁴³. The sample size for this study is based on an estimated reduction of 1.5 standard drinks with an estimated standard deviation (2.1) of the between Challenge Trial differences in alcohol self-administration, with an effect size

The Effects of Exenatide, a GLP-1 Agonist, on Alcohol Self-Administration in Heavy Drinkers
Version 1.8 10.5.20

of this magnitude (i.e. 0.7). This requires a sample size of 28 to allow for detection of a significant within-subject difference in alcohol consumption with an alpha value of 0.01 and power value of 0.81. Based on an estimated 15-20% rate of non-completion for randomized subjects, we anticipate randomizing 36 subjects to achieve a sample of 28 completers. Given our experience with recruiting AUD populations into clinical trials, we expect a screening exclusion rate of roughly 50%. Approximately 72 subjects will be consented and screened in clinic to yield a sample of 36 eligible subjects.

Given that this a laboratory based experiment we do not plan to conduct any planned interim analyses in this study.

13 Ethics/Protection of Human Subjects

This study is to be conducted according to applicable US federal regulations and institutional policies (which are based in federal regulations, guidance, and ICH Good Clinical Practice guidelines).

This protocol and any amendments will be submitted to the Boston Medical Center and Boston University Medical Campus IRB, for formal approval of the study conduct. The decision of the IRB concerning the conduct of the study will be made in writing to the investigator. A copy of the initial IRB approval letter will be provided to the sponsor before commencement of this study.

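### Eating before a subject's two challenge sessions is neither matched nor recorded, which may cost precision, mainly in the secondary 40-minute breath-alcohol AUC comparison (Hypothesis 3)

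*Combined protocol and SAP*

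**What the plan says.** Section 9 (Alcohol Challenge Trials 1 & 2) lists what is checked on arrival: "Concomitant medications, urine drug screening, Blood Alcohol Concentration (BAC) will be assessed to determine eligibility to proceed with the challenge". It adds a COVID-19 questionnaire, a BAC of 0.000 and a transport plan. It then fixes the timing of the injection, the priming drink and the two 60-minute drinking blocks. On absorption it says: "Subjects will be observed for 40 minutes following the priming dose of alcohol", with breath readings every 10 minutes.

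No part of Section 9 mentions a fast, a meal or the interval since last food. The CRF list in Section 11.3 and the schedules in Appendices A and B have no food item, and no analysis in Section 12.1 uses one.

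Food does appear elsewhere:
- Section 3.1 says that GLP-1 "regulates blood glucose by decreasing the rate of gastric emptying" and produces satiety.
- Section 6.1 cites nausea in 65% of healthy subjects after 10 mcg of exenatide "when they were allowed to eat a standardized meal 60 minutes after the administration of this drug".
- Sections 6.1 and 9 require a sugary mixer in the drinks.
- The exclusion criteria set a nonfasting glucose limit at baseline.

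Section 12.1 defines the outcomes at issue. Hypothesis 3 compares the 40-minute breath-alcohol AUC between the two sessions, and subjects with a nausea VAS above 30 are left out of the primary analysis.

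**The concern.** A crossover gains its precision because a subject's two sessions, here 7-14 days apart, differ in treatment and in as little else as possible. The plan holds the alcohol dose, entry BAC and timings constant but leaves stomach contents to chance. A subject may arrive fed for one session and fasted for the other.

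The most exposed measure is the Hypothesis 3 AUC. It is meant to show a drug effect on early alcohol absorption, and the mechanism the protocol gives for the drug is gastric emptying. Differences in eating would enter the SD of the within-subject AUC difference. As prior intake is not listed for recording, a noisy or null absorption result could not be examined for this explanation afterwards.

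Two further routes are weaker. Eating may affect how much a subject drinks, which is an inference from the stated satiety effect. It may also affect the nausea rating, and through the VAS cut-off decide whose data enter the primary analysis.

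**Working it through.** **1. The plan's own figure.** Section 12.2 states: "A group size of 28 completers was selected for use in this study". The effect size is 0.7, from an "estimated reduction of 1.5 standard drinks with an estimated standard deviation (2.1) of the between Challenge Trial differences", "with an alpha value of 0.01 and power value of 0.81". Sidedness is not stated.

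- Two-sided paired t-test, noncentral t, n = 28, d = 0.7: power 0.815. The stated 0.81 reproduces.
- With the unrounded ratio 1.5/2.1 = 0.714: power 0.834. This is the base for step 3.

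**2. How eating enters the variance.** Suppose eating state differs between the two sessions in a share q of subjects and shifts the outcome by δ. Sequence is randomised, so the shift is as likely to fall on one treatment as on the other. It adds zero on average to the treatment difference and q × δ² to the variance of the differences. The documents give neither q nor δ. I assume q = 0.25 to 0.50.

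**3. Drinking volume (primary).** Assumed δ = 0.5 or 1.0 drink, n = 28, two-sided alpha 0.01.

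Reading (a): the SD of 2.1 already contains the food noise, and matching removes it. SD = √(2.1² − qδ²).

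| δ | q | SD | Power (base 0.834) |
|---|---|---|---|
| 0.5 | 0.25 | √(4.41 − 0.0625) = 2.09 | 0.840 |
| 0.5 | 0.50 | √(4.41 − 0.125) = 2.07 | 0.846 |
| 1.0 | 0.25 | √(4.41 − 0.25) = 2.04 | 0.858 |
| 1.0 | 0.50 | √(4.41 − 0.50) = 1.98 | 0.883 |

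The gain is about 1 to 5 percentage points.

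Reading (b): 2.1 excludes the food noise. SD = √(2.1² + qδ²). With δ = 1.0 this gives 2.16 to 2.22, and power falls from 0.834 to 0.809 to 0.783. Section 12.2 says only that the effect size is "based on an assumed effect size of 0.7 suggested by similar alcohol self-administration studies" and does not describe the food rules of those studies, so the documents do not decide between (a) and (b).

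**4. Absorption AUC (secondary, Hypothesis 3).** Assumed δ = 30% of the AUC, and remaining SD of differences s = 20% or 30%. Inflation = √(s² + q × 0.30²) / s.

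| s | q | SD inflation |
|---|---|---|
| 0.30 | 0.25 | √0.1125 / 0.30 = 1.12 |
| 0.30 | 0.50 | √0.135 / 0.30 = 1.22 |
| 0.20 | 0.25 | √0.0625 / 0.20 = 1.25 |
| 0.20 | 0.50 | √0.085 / 0.20 = 1.46 |

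The SD is 12% to 46% larger. As required numbers scale with the variance, equal precision would take 1.12² = 1.25 to 1.46² = 2.1 times as many subjects.

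**The case against.** The strongest reply is that every food input above is assumed. The documents do not say how food changes alcohol absorption or how often a subject's sessions would differ. Under reading (a), the study meets its stated power with eating left uncontrolled, and a half-drink shift is worth only about one point. The larger inflation concerns a secondary outcome. All of this stands, and it keeps the point modest.

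A reader might infer more than the documents support:

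- **Bias.** Not supported. Sequence is randomised, and trial order is a covariate for Hypotheses 1 and 2. Eating before the session should not favour either treatment.
- **Harm to every outcome.** Too broad. Hypothesis 4 is a McNemar test on glucose below 50 mg/dl, so a larger SD of glucose does not enter it directly. The reading is also taken after drinks with sugary mixer whose amount depends on how much the subject drank. No figure supports an effect on craving.
- **Proof that meal timing drives nausea here.** Section 6.1 gives one rate at one meal time, after twice the study dose, and compares no timings. Its fasting evidence on alcohol and glucose concerns elderly diabetics on a sulfonylurea, and diabetics are excluded here. It also reports no more hypoglycemia with GLP-1 in fasting healthy subjects.
- **A need for equal clock times.** No passage links time of day to any outcome, and a list of CRF titles cannot show that start time goes unrecorded.
- **Unobserved eating during the blocks.** Section 9 provides for camera monitoring and video. The gap is food before the session.

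A participant instruction could sit in the consent pages, which were not available for this review. The protocol refers to none.

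**Conclusion.** The concern holds as an inexpensive improvement, mainly for Hypothesis 3. The protocol gives reasons to expect food to matter for early alcohol absorption, and its session procedures, CRF list and schedules neither match nor record prior intake. The cost is precision.

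Its size cannot be derived from the documents. The 12-46% AUC range rests wholly on the assumed discordance, shift and remaining SD. The effect on the primary comparison is small under the shifts considered: a gain of about 1 to 5 points if 2.1 already contains the noise, or a loss of about 2.5 to 5 points for a one-drink shift if it does not. The sample size arithmetic itself is sound. An influence of food on the nausea exclusion is plausible but unquantified.

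**What to change.** Add to Section 9 that each subject's two challenge sessions follow the same eating state and a similar interval since last food. Which state and interval is for the investigators to choose.

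Record the time and size of last intake on the CRF at each session, and add the item to Appendix A.

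Where a subject's two sessions still differ, use the recorded value in a supportive Hypothesis 3 analysis. It should be supportive only: if both sessions match, a fed/fasted term has no within-subject variation and cannot change the treatment contrast, so the gain comes from the matching.

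The cost is one line in the appointment instructions, one CRF item and slightly less flexible scheduling.
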